Study Protocol

UCI School of Medicine

Effectiveness of Onabotulinumtoxin A (Botox®) in Pediatric Patients Experiencing Migraines: A Randomized Double Blinded Placebo Crossover Study in the Pediatric Pain Population

[name], M.D., MBA
Director, Pain Services UCI Health

NCT03055767 | January 20, 2021

Upload this completed narrative and any supplemental documentation to the IRB Application .	IRB USE ONLY – HS#: 2016-3108
Lead Researcher Name: [name]	
Study Title: Effectiveness of Onabotulinumtoxin A (Botox®) in Pediatric Patients Experiencing Migraines: A Randomized Double Blinded Placebo Crossover Study in the Pediatric pain population	

CLINICAL TRIAL MASTER PROTOCOL AND INVESTIGATIONAL BROCHURE INFORMATION *

	Master Protocol	Investigator Brochure: <Specify Drug/Device>	Investigator Brochure: <Specify Drug/Device>	Sponsor Consent Form Template(s)
Version #:				
Version Date:				

This study is investigator-authored (investigator developed the study and is conducting the study at UCI and/or with other non-UCI sites).

* Add columns as applicable

NON-TECHNICAL SUMMARY

Provide a brief non-technical summary or synopsis of the study that can be understood by IRB members with varied research backgrounds, including non-scientists and non-affiliated members.
Headaches are traditionally characterized as acute, frequent, severe or throbbing/dull pain localized to the face or neck. Analgesics can be prescribed or acquired over-the-counter, depending on the severity of the ailment, as a common remedy to relieve pain and associated symptoms. Currently, preventative measures have emerged as a means to improve the quality of life of patients affected by neurological pain such as migraines. Botulinum Toxin Type A (Botox®), or onabotulinumtoxinA, is an FDA-approved neurotoxin developed by Allergan Inc. for treating chronic headaches and migraines in adults, however there is limited scientific literature on the outcomes of pediatric patients aged 8-17 receiving onabotulinumtoxinA. The purpose of this study is to determine the effectiveness of Botox® injections in pediatric patients for the treatment of chronic headache and common migraine in the pediatric population. We want to examine the long-term outcomes of patients who received onabotulinumtoxinA injections at UC Irvine Health for migraines and determine its effectiveness for pediatric pain use.

SECTION 1: PURPOSE AND BACKGROUND OF THE RESEARCH

1. Provide the scientific or scholarly rationale for the research. Describe the relevant background information and the specific gaps in current knowledge that this study intends to address.

Background

Chronic headache and migraine are one of the most common pain complaints in children and adolescents, both to the primary care provider, as well as to the pain physician specializing in pediatric pain disorders. Prevalence of migraine in younger children is approximately 10%, and up to 28% of adolescents suffer from recurrent headaches, the majority of which have migraineous features. [3,4] Aydin et al reported the most common headache presentation in pediatric neurology practices was migraine type, comprising 57.1% of all headaches presenting for initial consultation.[5] Population studies have demonstrated that over 130,000 school days are missed every two weeks and 3 million bedridden days occur per month as a result of pediatric migraine.[6] Common migraine is a debilitating disorder that requires both a plan to reduce the severity of attacks, as well as a prophylactic plan that reduces the frequency of occurrence. Episodic syndromes associated with migraine include recurrent gastrointestinal disturbance, cyclic vomiting syndrome and abdominal migraine, benign paroxysmal vertigo, and benign paroxysmal torticollis.[7] Powers et al demonstrated the negative impact of having childhood migraine on overall quality of life is similar to pediatric cancer, heart disease and rheumatic disease [8] As the frequency of migraine attacks increase, so does proportionally the child's disability in lost school time and family and social interactions, all of which may lead in turn to economic disability. Compared with episodic migraine sufferers, patients with chronic migraine have a lower socioeconomic status, reduced health-related quality of life, greater psychiatric and medical comorbidities, and increased occupational disability. [9] Stang et al estimated the health care costs are 70% higher for a family with a migraine than a non-migraine affected family, and direct medical costs for children with migraine are reported to be similar to those for adults. [6]. A study published in JAMA 2003 found that health care costs, work-related disability for parents and lost educational opportunity for the child leads to an annual economic impact in the US of approximately \$36 billion due to both direct medical costs and lost productivity into adulthood.[10]

OnabotulinumtoxinA

Botulinum neurotoxin-A is a purified neurotoxin complex produced by the anaerobic bacterium *Clostridium botulinum*. [11,12]. The main mechanism of action of botulinum toxin involved the targeting of the neuromuscular junctions by means of a specific cleavage of the soluble N-ethylmaleimide-sensitive factor (NSF)-attachment protein receptor complex (SNARE)-like synaptosomal-associated protein of 25kDa (SNAP-25) [11, 12]. The final outcome of this multi-step process is the inhibition of pain neurotransmission (i.e. Chemo denervation), including the inhibition of the release of migraine-related neuropeptides (eg CGRP and SP) and glutamate. [11,12,13]

OnabotulinumtoxinA was approved by the FDA in 2010 for adult patients with common migraine, with the indication of >15 headache days per month, with headache lasting 4 or more hours each day in people 18 years or older. BOTOX® prevents up to 9 headache days a month (versus up to 7 in placebo) and is injected every 3 months. [14,15]

While randomized, double blind, placebo-controlled trials evaluating OnabotulinumtoxinA efficacy in migraine prophylaxis in adult literature demonstrates statistically significant results towards safety and efficacy [14, 15], no such randomized, double blind placebo controlled data for safety or efficacy exists

in the pediatric population. In a retrospective case series by Ahmed et al to assess tolerability and efficacy of OnabotulinumtoxinA in 10 female patients aged 11-17 years, four patient reported subjective but clinically relevant relief in headache intensity, and 2 patients noting both decrease in intensity and frequency. The four responders also reported improvements in quality of life. [16] Chan et al prospectively evaluated 12 adolescent females with migraine and chronic daily headache, 6 of which were long term patients. They reported all long term patients had improvement in headache symptoms, which decreased on average 33-75%, and improvement in quality of life. [17] Kabbouche et al also in another retrospective study found statistically significant improvement in monthly headache frequency in 45 pediatric chronic daily headache patients who participated in 252 OnabotulinumtoxinA injections (average dose 188.5 +/- 32 units) and an improvement in pediatric migraine disability. A 30 point improvement in pediatric disability scoring between first injection and follow-up injection was also observed with decreased calculated disability from severe to moderate on PedMIDAS. [18] In a 10-year follow up of case series of OnabotulinumtoxinA intervention in adolescents with chronic daily headache and cervicalgia, Schroeder et al demonstrated both short term efficacy on headache frequency and severity, and in the long term follow up (10 years post injection therapy), chronic daily headache was not existent in any of the patients. [19] Common adverse events of OnabotulinumtoxinA reported in literature in the pediatric population are redness or temporary swelling at injection site, temporary pain at injection site, ptosis, and blurred vision [17]. In all of these studies, completion of a prospective, randomized double blinded placebo controlled trial is highly recommended to demonstrate objective outcome parameters in efficacy and tolerability. In the PI's nearly 5 year experience of using OnabotulinumtoxinA in pediatric practice she has seen dramatic improvement in patient pain (both in intensity and frequency of migraine), duration of action of migraine, school attendance, social interaction, disability and reaching student's intellectual potential by prophylactically treating headache with Botox.

Applications of Botulinum toxin A appears to be generally safe in the pediatric population for other indications, such as localized or segmental spasticity disorders, bladder hypertonicity, vestibular migraine as young as 2 years of age, although the majority of the class I and II studies included abobotulinumtoxinA (Trade name *Dysport*). [21] With the encouraging data in adults with chronic migraine presented at the 14th Congress of the International Headache Society (Philadelphia, PA 2009) and with the experiences of the above cited retrospective case series, it certainly appears reasonable to further explore a potential role for OnabotulinumtoxinA in the management of chronic migraine in the pediatric population.

2. Provide relevant preliminary data (animal and/or human).

Significance

While most chronic pain conditions are manageable, migraine pain can be devastating. Recently, OnabotulinumtoxinA was approved for the prophylaxis of migraine symptoms by the US Food and Drug Administration (FDA), which has dramatically altered the way pain physicians approach migraine pain. Unfortunately, most adults who suffer with migraines have their first headache during childhood or adolescence [1]. Although it appears that many preventative agents are safe in children, none are currently FDA-approved for this age group. As a result, despite experiencing significant disability, the vast majority of children who present to their physician with migraine headache do not receive prophylactic therapy. [2]

Treatment for pediatric head pain is an extrapolation from all that we have learned about adult headache with the expertise of working with children in pain. Pediatric pain medicine historically has its

own challenges, largely suffering from under-assessment or treatment paradigms extrapolated from adult literature. Current clinical studies, while able to demonstrate efficacy, may not demonstrate safety, or vice versa.

The significance of this study is to evaluate the efficacy of OnabotulinumtoxinA (BOTOX®) for the treatment and prophylaxis of pediatric migraine in a randomized, double-blinded, placebo cross over study. No trials currently exist in literature studying OnabotulinumtoxinA for efficacy and/or safety for indication of pediatric migraine, although significant contributions have been made by retrospective case series over the last 10 years. The historical and longitudinal context of the interest to design this study comes from the Principal Investigator's (PI) extensive use of "off label" OnabotulinumtoxinA to treat refractory pediatric migraine over the last 5 years. Anecdotally, the results are so impressive and impactful in her patients' lives, that this therapeutic ought to be studied in a controlled setting to demonstrate clinical outcome to validate existing treatment strategies. Thus, this study seeks to fulfill ASRA's goal of identification of novel applications of existing therapeutics. Moreover, this trial may benefit an under-studied pain population with the long-term goal of new FDA indication to "on label" status. The proposal also carries policy and legislative impact as it fulfills the federal initiative to design and conduct trials in the pediatric pain population within confines of the Best Pharmaceuticals for Children Act (BPCA) of 2002. The goal of the BPCA Program is to improve pediatric therapeutics through preclinical and clinical drug trials that lead to drug labeling changes.

3. Describe the purpose, specific aims or objectives. Specify the hypotheses or research questions to be studied.

Specific Aims

The proposed research is intended to explore whether pediatric chronic migraine may benefit from OnabotulinumtoxinA treatment. The study is focused on a specific debilitating disorder of chronic pain in a well-defined population that is historically not well studied. The objectives are attainable within the proposed timeframe.

Hypothesis:

Aim 1: To test if OnabotulinumtoxinA is superior to placebo in reducing headache frequency, intensity and pediatric migraine-related disability (Efficacy)

Aim 2: To evaluate the incidence of adverse events of OnabotulinumtoxinA administration in children aged 8-17 (Safety, Tolerability)

Aim 3: To evaluate if OnabotulinumtoxinA can contribute to reduction in preventive and rescue medication, reduction in health care utilization via emergency room and hospital admissions and health care costs (Hospital and pharmacy resource utilization)

Study aims fit together in an overall framework such that primary and secondary outcomes are easily defined, measureable, and validated as an acceptable means to measure clinical success and to longitudinally assess response.

4. Describe the primary outcome variable(s), secondary outcome variables, and predictors and/or comparison groups as appropriate for the stated study objectives/specific aims.

Primary outcome: Absolute number of headache days per month.

Secondary outcomes

- Severity of headache episode
- Disability scoring (PedMIDAS)
- Duration of benefit assessed at every 6 week interval
- Change from baseline in the frequency of severe headache days
- Change from baseline in the total cumulative hours of headache on headache days Change from baseline in the total dose or interval of preventive migraine or rescue migraine medication
- Percentage of patients with $\geq 50\%$ decrease from baseline in the frequency of headache days
- Percentage of patients who are prescribed oral rescue migraine prophylactic treatment
- Percentage of patients who reduce consumption of preventive migraine or rescue migraine treatment
- Change from baseline in the absolute ED visits and/or hospital admission during each treatment phase
- Percentage of patients experiencing associated adverse events, serious or non-serious. (Non-serious defined as injection site swelling, redness, temporary pain, ptosis, blurred vision, worsening of migraine, nausea, vomiting, head lag weakness, drooling.)

5. List up to ten relevant references/articles to support the rationale for the research. Do not append an extensive NIH-grant-style bibliography.

1. Aurora, S.K., et al., *OnabotulinumtoxinA for treatment of chronic migraine: pooled analyses of the 56-week PREEMPT clinical program*. Headache, 2011. **51**(9): p. 1358-73.
2. Dodick, D.W., et al., *OnabotulinumtoxinA for treatment of chronic migraine: pooled results from the double-blind, randomized, placebo-controlled phases of the PREEMPT clinical program*. Headache, 2010. **50**(6): p. 921-36.
3. Ahmed, K., et al., *Experience with botulinum toxin type A in medically intractable pediatric chronic daily headache*. Pediatr Neurol, 2010. **43**(5): p. 316-9.

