Specify where the research procedures will take place (e.g. UCI Douglas Hospital – Cardiac Care Unit, UCI Main Campus Hewitt Hall, UCI Health – Pavilion II, UCI Family Health Center, Anaheim, Irvine High School).

If research activities will also be conducted at non-UCI locations (e.g., educational institutions, businesses, organizations, etc.), Complete Appendix A. Letters of Permission or other documentation may be required (e.g. Off-site Research Agreements or IRB Authorization Agreements).

The research procedures will take place at UC Irvine Medical Center in the Medical Specialties facility and Gottschalk Medical Plaza on UCI main campus. Any data obtained for the study will be stored in a secure, locked facility in the UCI Anesthesia Research Department for the duration of the study.

B. Study Design

1. Include an explanation of the study design (e.g., randomized placebo-controlled, cross-over, cross-sectional, longitudinal, etc.) and, if appropriate, describe stratification/ randomization/blinding scheme.

Study Protocol

After enrollment, each subject will begin with a 28 day baseline screening phase followed by a 24 week double-blind, placebo-controlled, randomized AB|BA crossover period as the primary study protocol, followed by a second 24-week open-label period where all subjects will receive treatment with OnabotulinumtoxinA as follow-on treatment. There will be one treatment every 12 weeks, meaning 4 treatment blocks over the 48 week study period total. Those assigned to the AB group will receive OnabotulinumtoxinA in the first treatment and saline placebo in the second, while those in the BA group will receive saline and then OnabotulinumtoxinA. Both groups will then receive OnabotulinumtoxinA in the last two treatments. Progress check-ups will occur every 6 weeks during the study. Twelve week blocks were specifically selected in order to minimize carry-over effects from treatment periods, as the clinical efficacy of OnabotulinumtoxinA is nearly gone after twelve weeks in the PI's experience and reported literature.

Randomization will be via selection of sealed envelope. Injections will be performed at fixed-site, fixed-dose locations at 31 sites recommended by the PREEMPT 1 and 2 studies, including procerus, corrugators, frontalis, temporalis, occipitalis, splenius capitis, and trapezius muscle beds. At the

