investigator's discretion, an additional 40U may be administered using a follow-the-pain strategy. The maximum dose will be **155 U across 31 sites**. All treatments will be performed by the PI.

2. Provide precise definitions of the study endpoints and criteria for evaluation; if the primary outcomes are derived from several measurements (i.e., composite variables) or if endpoints are based composite variables, then describe precisely how the composite variables are derived.

Primary outcome variables:

- Pain scores: as a standard part of the procedure, patients are asked to record their pain scores before and after their procedure. The principal endpoints are intensity on a 10 point NRS scale (VAS where needed), and frequency of migraine episodes in a 30 day period. This will be compared to baseline data pre-injection. For the study, pain score data will be collected up until the last follow up of the last injection of each patients' Botox ® injection series.
- Duration of benefit from the Botox ® injections: reduction in pain score by greater than or equal to 30%
- Functionality: the extent of normal activity able to be performed by a patient
- Disability: inability to function normally, physically or mentally
- Opioid consumption: amount of opioid medication consumed
- Neuropathic/migraine medication consumed including immediate release NSAID

Secondary outcome variables:

- Quality of pain: continuous, intermittent, throbbing, etc.
- Associated side effects: nausea, vomiting, food intake, diarrhea, constipation, anxiety, depression and/or adverse events associated with study drug
- Psychological history i.e. anxiety, depression
- Neuropathy: any weakness, numbness, and pain from nerve damage, usually in the hands and feet
- Type of analgesia/anesthesia: analgesic/anesthetic medication(s) used during procedure

Incidence of hospital admissions

- Incidence of ER visits
- Current medication use

Other variables:

- Neurological workup: Neurological medical evaluation, including medical history, physical examination, medical tests, survey of the patient's medical record for any information regarding Neurological disease
- Diagnosis: identification of chronic migraine head pain
- Indications: reason for Botox ® injections, number of injections in the Botox ® injection series
- Procedure: specific procedure including location of procedure, imaging information, and other specific procedure information

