Our primary endpoint will be the same as that used in the PREEMPT trial which examined the efficacy of OnabotulinumtoxinA in adult patients [1, 2]. Specifically, we will look for a reduction in frequency of headache days per month, as well as decrease in intensity utilizing a 10 point NRS scale (VAS when appropriate). In that trial, at baseline, patients reported 19.9 ± 3.6 headache days per month. The treatment group showed a reduction of 8.4 days, and the placebo group a reduction of 6.6 days (standard deviations on these reductions were not reported). Interpretation of the data was complicated by the medication regimens the patients were on at baseline (which frequently included over-use of opioid medications).

2. Describe the primary statistical method(s) that will be used to analyze the primary outcome(s) or endpoints.

Design considerations: Given the evidence of efficacy in the available scientific data and the PI's extensive personal experience in the pediatric population (where it has been found to be life-changing), prolonged withholding of OnabotulinumtoxinA for the purpose of study was not considered reasonable by the PI. Thus, a study design minimizing the placebo control period while still allowing for comparison of OnabotulinumtoxinA to a control group was desirable. An AB|BA cross-over design (which uses each patient has his/her own control, both minimizing recruitment numbers and the need for a control group which never receives treatment with OnabotulinumtoxinA), was selected as the best option. A four week baseline prior to treatment will act as a no-treatment control to compare to both the treatment and placebo.

The primary outcome will be the difference between treatment and placebo injections on headache frequency. The difference will be calculated as

$$(A_A - A_B) - \frac{1}{2} (A_A - A_B)$$

Where λ represents possible carry-over effects from the previous treatment period. Because the cross-over period is uniform and balanced, we will assume that period effects and sequence effects are aliased out. The treatment and placebo effects will be calculated as:

$$\hat{\mu}_A = \frac{1}{2}(\bar{Y}_{AB,1} + \bar{Y}_{BA,2}) \text{ and } \hat{\mu}_B = \frac{1}{2}(\bar{Y}_{AB,2} + \bar{Y}_{BA,1})$$

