1. Describe and assess any reasonably foreseeable risks and discomforts — physical, psychological, social, legal or other. Include an assessment of their expected frequency (e.g., common – 65%, less common – 40%, unlikely – 5%, rare - <1%) and the seriousness (mild, moderate, severe). A *bullet point list is recommended. If this study will involve the collection of identifiable private information, even temporarily, for which the disclosure of the data outside of the research could reasonably place the subjects at risk, include the risk of a potential breach of confidentiality.*

As listed in the Risks section of the Informed Consent.

2. Discuss what steps have been taken and/or will be taken to prevent and minimize any risks/ potential discomforts to subjects. *Examples include: designing the study to make use of procedures involving less risk when appropriate; minimizing study procedures by taking advantage of clinical procedures conducted on the subjects; mitigating risks by planning special monitoring or conducting supportive inventions for the study; implement security provisions to protect confidential information.*

All extracted data will be de-identified immediately and save on a secured database for research purposes only. Study team members will follow strictly the reporting guideline by IRB in case of a breach of confidentiality, which is nearly impossible since all data are de-identified. Regardless, all collected information will be securely stored on a password-protected server.

Subjects for this study will be closely monitored for any potential adverse events. Subjects will be able to call the Lead Researcher 24 hours a day for any potential issues.

C. Potential Benefits

1. Describe the potential benefits subjects may expect to receive from participation in this study. *Compensation is not a benefit; do not include it in this section.*

There is no direct benefit anticipated for the subjects.

There is a prospect of direct benefit to children participating in the study. Taking part in this study may or may not make your health better with the first two treatments. While researchers hope Botox® will be more effective than the standard (usual) treatment, there is limited proof of this yet.

2. Specify the expected potential societal/scientific benefit(s) of this study.

Overriding Rationale

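### The safety outcome counts only undefined 'associated' adverse events, and no Botox-versus-saline comparison of them is planned

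*Combined protocol and SAP*

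**What the plan says.** The safety outcome is the last secondary outcome in Section 1, item 4: "Percentage of patients experiencing associated adverse events, serious or non-serious". A parenthesis follows it: "Non-serious defined as injection site swelling, redness, temporary pain, ptosis, blurred vision, worsening of migraine, nausea, vomiting, head lag weakness, drooling". Serious events have no corresponding list.

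Section 6.B, item 2 words the outcome differently. Under side effects it names nausea, vomiting, food intake, diarrhea, constipation, anxiety and depression, and then adds, joined by and/or, "adverse events associated with study drug".

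Aim 2 (Section 1, item 3) is "To evaluate the incidence of adverse events of OnabotulinumtoxinA administration in children aged 8-17". Section 7.B, item 2 says subjects will be closely watched for adverse events and attaches no qualifier about cause.

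The design has a "24 week double-blind, placebo-controlled, randomized AB|BA crossover period as the primary study protocol", followed by 24 weeks in which every child knowingly receives Botox. The outcome does not say which phase it covers. Section 6.I, item 3, which asks for the methods for secondary outcomes, is answered as not applicable.

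**The concern.** Section 7 gives the demonstration of safety and tolerability as part of the trial's overriding rationale, and Section 1 says that no randomised pediatric data exist. The design provides a blinded saline block for each child. A comparison of all adverse events between the Botox and saline blocks would use it without needing anyone's opinion on cause.

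The outcome as worded does not secure that comparison. A qualifier that nobody has defined decides what is counted, and two sites of the plan give different examples. If the qualifier is applied as a drug-relatedness filter, the conditions for applying it change at week 24, when treatment becomes known. The rate reported could then differ between phases for reasons unrelated to tolerability. If all 48 weeks are pooled, which the wording allows, saline time and open-label time are mixed in one percentage.

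**Working it through.** **The plan's own figure.** There is none for adverse events. The only powered figure is 13 per group (26 in total) for headache days. It reproduces: d = (8.4 − 6.6)/1.35 = 1.33, and a two-sided two-sample t-test at 0.05 with power 0.90 needs 12.86, so 13 per group, with power 0.903. It does not bear on this point except by fixing the number of children at 26.

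**The two event lists.** Section 1, item 4 names ten non-serious events and Section 6.B, item 2 names seven. Only nausea and vomiting are in both. Ptosis, blurred vision, drooling, head lag weakness, worsening of migraine and the injection-site events are missing from the second list. Diarrhea, constipation, food intake, anxiety and depression are missing from the first.

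**The two readings of *associated*.**

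- *Drug-related*, as the Section 6.B wording suggests. Someone must attribute each event, under blind in weeks 0-24 and with treatment known in weeks 24-48.
- *On the list.* No attribution is needed for the listed events, but a non-serious event outside the list is not counted. Serious events have no list, so *associated* remains their only filter.

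Either way, the outcome is narrower than the monitoring in Section 7.B.

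**Illustration of shrinkage (all rates assumed).** Let the true percentages with any event be p₁ = 40% on Botox and p₀ = 20% on saline. Let a share *a* of events be judged associated, the same in both blocks, as would be expected under effective blinding. With one event per affected patient, the observed difference is a(p₁ − p₀). With two events per affected patient, judged independently, a patient counts if either qualifies, so the multiplier is 1 − (1 − a)².

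| a | One event each: a × 0.20 | Two events each: [1 − (1 − a)²] × 0.20 |
|---|---|---|
| 1.0 | 0.20 | 0.20 |
| 0.8 | 0.16 | 0.96 × 0.20 = 0.192 |
| 0.5 | 0.10 | 0.75 × 0.20 = 0.15 |
| 0.3 | 0.06 | 0.51 × 0.20 = 0.102 |

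The ratio p₁/p₀ stays at 2 in every row. The absolute difference and both incidences shrink.

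**Illustration of a shift at week 24 (assumed).** Take an unchanged true incidence of 30% and one event per affected patient. If 70% of events are attributed while blinded and 50% when open, the reported rate goes from 0.30 × 0.70 = 21% to 0.30 × 0.50 = 15%. If the shares are reversed, it goes from 15% to 21%. The documents do not say which is more likely.

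**What 26 children can show.** The chance of seeing at least one case of an event with a true rate of 2%, 5% or 10% is 1 − (1 − r)²⁶ = 0.41, 0.74 or 0.94. No events in 26 leaves a one-sided 95% upper bound of 1 − 0.05^(1/26) = 10.9%. An exact McNemar test between blocks needs at least six discordant children, all in one direction, to fall below 0.05 (2 × 0.5⁶ = 0.031; with five it is 0.0625).

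**The case against.** A reader might infer something stronger: that safety rests on the investigator's causality judgement in place of the randomised comparison, and that this judgement will favour the drug. The plan states that "All treatments will be performed by the PI" and that "Subjects will be able to call the Lead Researcher 24 hours a day for any potential issues", and it cites "the PI's extensive personal experience in the pediatric population (where it has been found to be life-changing". None of these statements assigns the attribution of adverse events to anyone. No causality step, scale or assessor is described in the text at hand. Section 2 on the study team and the consent form's risk section could not be consulted, so the absence of a named assessor proves nothing. Nor does the plan choose attribution over randomisation; it specifies no comparison of adverse events at all.

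The list in Section 1 also cuts against the stronger reading. It names worsening of migraine, nausea and vomiting, so events that resemble the disease are expected to count. The and/or in Section 6.B lets the named symptoms be recorded without attribution. Aim 2 is no clear contrast either, since events *of* Botox administration can itself be read as attributed. Finally, attribution made under blind should act alike on both blocks, so it weakens the randomised contrast without destroying it.

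All of this stands. What it leaves untouched is that the term is undefined, the lists conflict, the phase is unstated, no comparison is planned, and both available readings omit events that the trial will already be watching for.

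**Conclusion.** The point holds as a defect of definition and analysis. The outcome can understate incidence and shrink the absolute Botox-saline difference. In the illustration the difference falls from 0.20 to between 0.06 and 0.192, depending on the share attributed and the number of events per child. Those figures rest on assumed rates and on equal attribution in both blocks. The documents support neither a size nor a direction for any change between the blinded and open-label phases, so a claim that tolerability will look falsely better, or falsely worse, on repeat dosing is not warranted. The primary headache outcome is unaffected. The change is worth making because it is cheap and uses events that are already to be monitored.

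**What to change.** 1. In Section 1, item 4, replace the outcome with: *percentage of patients with any adverse event, serious or non-serious, regardless of relationship to study drug*. Align Section 6.B, item 2, and reconcile the two lists as examples of events, so that neither limits what is counted.
2. In Section 6.I, item 3, state that this percentage will be reported by treatment received (Botox or saline) within the 24-week blinded crossover, as the comparative safety result. Show the open-label 24 weeks separately.
3. Keep any relatedness rating as a secondary attribute in its own table. State who rates it and under what blinding, and for the blinded blocks require entry before unblinding.

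The cost is one outcome definition, one case report form field and one extra table. Reported percentages will rise because unrelated events are included in both blocks. The comparison stays open to carry-over from Botox into the saline block in the AB sequence, and 26 patients remain uninformative about rare events.
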